#### 10.2. Handling of stops and dropouts

In the event of discontinuation or withdrawal from the study, the principal investigator or person in charge shall discontinue the administration of the investigational drug and record the date of discontinuation and withdrawal, reason for discontinuation and withdrawal, along with all data obtained up to the time of discontinuation and withdrawal in the supporting documents and CRF. In particular, if the patient does not visit the clinic during the study, the reason for and future progress will be followed up through e-mail, telephone, etc., and progress will be recorded in the CRF. The results of the clinical trial obtained up to the time of discontinuation or dropout may be reviewed for evaluable items during the final evaluation.

## 11. Data Analysis & Statistical Considerations

#### 11.1. Sample size calculation

This is an exploratory study to determine the effectiveness of medication in improving venous reflux in patients with varicose veins, and there are limited prior studies to draw upon. Therefore, the study design is based on some assumptions, and it is not advisable to apply the same process to calculate the number of participants that are required to meet the mathematical basis for a confirmatory study when controlling for type 1 and type 2 errors.

Nevertheless, a few assumptions can be made to develop a power-calculation process similar to that of a confirmatory study. According to the literature, the duration of reflux was measured slightly differently at each point, and we calculated the number of participants based on the GSV, prox, which had the largest number of patients (Reference: J Vasc Surg. 2004 Aug;40(2):303-10.). In this study, we examined the difference between the means, but we could not find any evidence; therefore, we used the median value of the references as the mean. This assumes that n is sufficiently large (174), according to the principle of the central limit theorem, so the gap between the median and mean is not large. We also calculated the standard deviation using the range and number of n. By calculating the standard deviations of the other parameters together, we found that the standard deviation of the valve-carrying segments can be assumed to be approximately 1.8 overall. The results of the drug group are expected to improve by approximately 10% to 15%; therefore, we decided to conservatively assume an improvement of 12.5% to calculate the number of participants.

Valve-carrying	n	Median (s)	Range (s)	sd
segment				
GSV, prox	174	6.1	0.7-10.0	1.737
GSV, dist	84	3.5	0.7-10.0	1.921
SSV	91	4.6	0.6-10.0	1.918

In this case, assuming a normal distribution and based on a Z-test with the same variance in both groups, the following calculation result was obtained under  $\alpha$ =0.025,  $\beta$ =0.2. The calculations were performed using the PASS15. A one-tailed test was performed to determine superiority if the difference between the drug and lifestyle treatment groups was less than zero. Assuming that patients may drop out during the study, the dropout rate was set at 20% to account for dropouts in a typical clinical setting. Therefore, the total number of participants was calculated as 160, with 80 participants in each group. Considering a dropout rate of 20%, we plan to recruit 200 participants, 100 in each group, to conduct the study.

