## 4. Research protocol and trial design

This study is designed as an investigator-initiated, single-center, open-label, pragmatic, randomized controlled trial. Patients with symptoms of lower extremity discomfort and leg edema and demonstrable venous reflux on lower extremity venous Doppler ultrasound ( $\geq 0.5$  seconds in superficial veins or  $\geq 1$  s in deep veins) will be screened for inclusion in the study. All patients who meet the inclusion criteria will be considered for inclusion.

[figure not shown]
Patients who are eligible for randomization will be randomized 1:1 to the therapeutic lifestyle change (TLC) only arm (control arm) or the medication (Entelon®) plus TLC arm (test arm). The patients will be treated for 12 weeks according to their assigned treatment arms. Patients will be evaluated for improvement in venous reflux in the target vessels and symptomatic improvement using lower-extremity venous Doppler ultrasonography at 6 and 12 weeks post-treatment.

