#### 4.3. Therapeutic lifestyle changes group

Implementing TLCs is a critical component of a comprehensive treatment plan for varicose veins. These non-invasive interventions focus on amending daily habits and behaviors that contribute to the progression of the condition and exacerbation of symptoms. A key aspect of TLCs is the optimization of postural habits. Patients are advised to avoid extended sitting or standing periods, which exert additional pressure on the venous system in the lower extremities and exacerbate venous insufficiency. During rest periods, elevating the legs closer to the heart is recommended because this simple yet effective adjustment promotes venous return and reduces the gravitational burden on the venous valves of the legs. The use of graduated compression stockings during waking hours is another therapeutic lifestyle intervention that is often prescribed for patients with varicose veins. These stockings exert the highest amount of pressure on the ankle, with the pressure gradually decreasing up the leg, thereby mimicking the

physiological pumping function of the calf muscles. This supports the veins in pushing blood back towards the heart, improving overall blood circulation and reducing leg swelling and discomfort associated with varicose veins.

Additional TLCs include maintaining optimal body weight and engaging in regular physical exercise. Being overweight or obese can increase intra-abdominal pressure, which can impose an additional burden on the leg veins. Regular physical activity, specifically exercises that engage the calf muscles, can improve muscle tone, enhance the efficiency of the calf muscle pump, and consequently, improve venous return. Walking or cycling are often recommended because of their effectiveness in promoting lower limb venous return.

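### The 12.5% improvement called conservative is the middle of the plan's own range and was rounded up to 13.1%; power is 76% at 12.5% and 57% at 10%, and the plan does not say whether the improvement is over and above lifestyle change

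*Combined protocol and SAP*

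**What the plan says.** Section 11.1, and Section 1 in nearly the same words, build the planned effect in three steps.

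- **Control mean.** The proximal great saphenous vein median from one cited study, 6.1 s, stands in for a mean: "therefore, we used the median value of the references as the mean".
- **Improvement.** The results of "the drug group are expected to improve by approximately 10% to 15%; therefore, we decided to conservatively assume an improvement of 12.5" per cent.
- **SD.** From ranges and sample sizes in the same source, "the standard deviation of the valve-carrying segments can be assumed to be approximately 1.8 overall".

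The PASS output in Section 1 enters 5.3 s for the drug arm and 6.1 s for the TLC-only arm, a difference of -0.8 s, with SD 1.8 s and one-sided alpha 0.025. Section 11.1 states the test as follows: "A one-tailed test was performed to determine superiority if the difference between the drug and lifestyle treatment groups was less than zero". The result is that "the total number of participants was calculated as 160, with 80 participants in each group", and then: "Considering a dropout rate of 20%, we plan to recruit 200 participants, 100 in each group, to conduct the study".

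Both arms receive TLC, including compression stockings (Sections 4.3 and 4.4). Section 4.3 says of the stockings: "This supports the veins in pushing blood back towards the heart, improving overall blood circulation and reducing leg swelling and discomfort". Section 9 says that such measures do not cure but can help the circulation. Neither section gives an expected effect of TLC on reflux time.

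**The concern.** A planning effect is conservative when it lies towards the small end of what is expected, because a smaller effect needs more patients. The value here is mid-range and was then rounded in the favourable direction. A reader of Section 11.1 would take 80% power to be secured at a cautious effect. In fact it belongs to an effect above the percentage named.

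The second issue is what the improvement is measured against. It is attributed to the drug group, which also receives TLC, while the TLC-only arm is held at the literature value. The trial can detect only the excess of drug plus TLC over TLC alone. The plan does not say that the 12.5% is that excess.

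What is at stake is how the result is read. If the true difference were 10%, which the plan itself regards as plausible, the trial would miss it more than four times in ten. The plan's description of its power gives no warning of this.

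**Working it through.** **Inputs, all from Sections 1 and 11.1:** control mean 6.1 s; drug-arm mean 5.3 s; SD 1.8 s; 80 evaluable per arm; one-sided alpha 0.025 (z = 1.96); z-test with equal variances; dropout 20%.

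**Formulas.** Standard error = 1.8 × √(2/80) = 0.2846 s. Power at difference d = Φ(d/0.2846 − 1.96). Patients per arm for 80% power = 2 × (1.96 + 0.8416)² × 1.8²/d² = 50.86/d², rounded up.

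**Step 1: reproduce the plan.** At d = 0.8, 0.8/0.2846 − 1.96 = 0.851, so power is 80.3% (PASS: 0.80260). Patients per arm: 50.86/0.64 = 79.5, so 80; and 80/0.8 = 100 enrolled per arm. The plan's figures reproduce exactly.

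**Step 2: compare the percentage with the seconds.** The midpoint of 10% and 15% is 12.5%. 12.5% of 6.1 s is 0.7625 s, which would put the drug arm at 5.3375 s; the plan enters 5.3 s. The 0.8 s used is 0.8/6.1 = 13.1%.

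**Step 3: power across the plan's own range, control arm at 6.1 s.**

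| Improvement | d (s) | Power, 80 per arm | Per arm for 80% | Enrolled in total with 20% dropout |
|---|---|---|---|---|
| 10% | 0.61 | 57.3% | 137 | 344 |
| 12.5% | 0.7625 | 76.4% | 88 | 220 |
| 13.1% (as entered) | 0.80 | 80.3% | 80 | 200 |
| 15% | 0.915 | 89.5% | 61 | 154 |

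This table needs no input from outside the plan.

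**Step 4: the two readings of the improvement.**

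*Excess over TLC.* If TLC shortens reflux by the same number of seconds in both arms and the drug adds 0.8 s, the difference is still 0.8 s and power is still 80.3%. If instead the drug's excess is 13.1% of a mean that TLC has already lowered by an assumed 5%, d = 0.1311 × 5.795 = 0.76 s and power is 76.1%.

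*Total change of the drug arm.* With that arm fixed at 5.3 s, any TLC-only improvement comes off the difference. The documents give no TLC effect on reflux time, so the range below is assumed.

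| Assumed TLC-only improvement | d (s) | Power |
|---|---|---|
| 0% | 0.80 | 80.3% |
| 2.5% (0.1525 s) | 0.6475 | 62.4% |
| 5% (0.305 s) | 0.495 | 41.3% |

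**The case against.** **The effect is already defined between the arms.** Section 1 gives PASS a difference of two arm means, and Section 11.1 names it as the difference between the drug and lifestyle groups. That stands: the calculation addresses the right comparison. What is missing is the basis for the size of the difference, and a statement that the drug-group improvement is beyond TLC.

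**A reader might infer that 80% power holds only if lifestyle change does nothing to reflux.** The documents do not support this. Both arms receive TLC, and an equal effect in seconds with a 0.8 s drug increment leaves power at 80.3%. The inference needs the improvement to be the drug arm's total change. The wording and the two means lean that way but do not settle it. Nor do the documents say that TLC shortens reflux time; Section 4.3 speaks of venous return, circulation, swelling and discomfort.

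**A reader might also call 6.1 s an untreated value.** The documents do not give the treatment status of the cited patients. It is a literature value to which no change was applied.

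**The study is called exploratory.** Sections 1 and 11.1 admit limited prior data and reliance on assumptions. This lowers the stakes and is a reason to leave N alone. But the plan then presents a calculation resembling a confirmatory one and reports 80% power, so label, percentage and power should agree.

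**12.5% is conservative compared with 15%.** True, but the same range makes it optimistic compared with 10%, and the rounding moved it further up.

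**The SD is itself doubtful.** It comes from ranges of raw reflux times, while the primary endpoint (Section 3.3) is change from baseline, and no SD of change is given. This stands. It applies equally to the plan's 80% and to every figure above.

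**Conclusion.** The point holds in two parts.

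The first is an error on the plan's own figures. The assumed improvement is mid-range, not conservative, and the 80.3% power belongs to 13.1%. At the stated 12.5% power is 76.4%, and at the lower end of the expected range it is 57.3%. These results take the plan's SD of 1.8 s, its z-test and 80 evaluable patients per arm as given.

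The second is an ambiguity. The plan does not say whether the improvement is the drug arm's total change or its excess over TLC. Under an excess of 0.8 s nothing is lost; under the total-change reading power could fall to 62% or 41%. Those two values are illustrations that rest on an assumed TLC effect, and should be labelled so wherever they are used.

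A reader might want to add that a non-significant result would not exclude differences below 0.8 s. That would mislead, because it suggests that larger differences are excluded. With a standard error of 0.285 s, an estimate just short of significance is about 0.56 s, and its upper 95% limit is about 0.56 + 0.56 = 1.1 s. Only the confidence interval shows what a given result excludes.

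**What to change.** In Sections 1 and 11.1:

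1. Delete *conservatively*, and say that 12.5% is the midpoint of the expected range.
2. Make effect and power agree: either give power as about 76% at 12.5% (0.7625 s), or keep 80% and state that 0.8 s is 13.1% of 6.1 s.
3. Report power of 57% at the lower end of the range (10%, 0.61 s).
4. State that 0.8 s is the between-arm difference over and above TLC. If that is not what was meant, state and justify the change assumed in the TLC-only arm. Any power shown for a TLC-only improvement should be marked as resting on an assumed value.
5. Note that all these figures depend on the SD of 1.8 s, which was derived from raw reflux times and not from changes.

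In Section 11.2, add that a non-significant primary result will be interpreted from the confidence interval for the between-arm difference.

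N stays at 200, and nothing in the conduct of the trial changes. The cost is a few sentences and a short power table, and a stated power that looks less favourable.

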#### Sample size

#### 200 patients

# Sample size calculation

This study is an exploratory study to determine the effectiveness of venous reflux improvement after medication in patients with varicose veins, and there are limited prior studies to draw upon. Therefore, the study design is subject to a number of assumptions. In addition, it is not advisable to apply the same process for calculating the number of patients to meet the mathematical basis for a confirmatory study as for a confirmatory study when controlling for type 1 and type 2 errors.

Nevertheless, a few assumptions can be made to develop a power calculation process that is similar to that of a confirmatory study. According to the literature, the duration of reflux was measured slightly differently at each point, and we would like to calculate the number of

patients based on GSV, prox, which had the largest number of patients (Reference: J Vasc Surg. 2004 Aug;40(2):303-10.). In this study, we would like to conduct an analysis on the difference between the means, but no relevant evidence was found; therefore, we borrowed the median value of the references as the mean. This assumes that the number of n is large enough (174) according to the principle of central limit theorem, such that the gap between the median and the mean is not large. We also calculated the standard deviation using the range and the number of n. By calculating the standard deviation of other parameters together, we found that the standard deviation of the valve-carrying segments can be assumed as approximately 1.8 overall. The results of the drug group are expected to improve by about 10% to 15%, and we decided to conservatively assume an improvement of 12.5% to calculate the number of patients.

Valve-carrying	n	Median (s)	Range (s)
segment			
GSV, prox	174	6.1	0.7-10.0
GSV, dist	84	3.5	0.7-10.0
SSV	91	4.6	0.6-10.0

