#### 11.2. Statistical analysis plan

Categorical variables will be expressed as percentages and numbers and will be compared using the Chi-square or Fisher's exact test. Continuous variables will be presented as means, standard deviations, medians, and interquartile ranges and will be compared using an independent two-sample t-test or Wilcoxon rank sum test, while the normality of the underlying variable distribution will be estimated using histograms, skewness, kurtosis, and the Kolmogorov-Smirnov test.

The primary outcome will be presented and compared between the two groups using an independent two-sample t-test. Normality of the empirical distribution of the primary outcome will be evaluated. If this assumption is violated, a nonparametric Wilcoxon rank-sum test will be used. Secondary outcomes will also be summarized and compared between groups using independent two-sample t-tests for continuous outcomes, or chi-square test or Fisher's exact test for categorical outcomes. Considering the factors that may influence the outcome, aside from the randomly assigned intervention, we will conduct an analysis involving the adjustment of the baseline characteristics for primary and secondary outcomes. This careful analytical strategy ensures that our findings are not confounded by pre-existing differences, thereby allowing us to assess the true impact of the intervention more accurately. A planned, exploratory subgroup analysis will be performed to compare the treatment effect in patients with vericose veins with and without Entelon® medication. Unless otherwise specified, all tests will be performed at a significance level of 0.05. All analyses will be performed using SAS 9.4 (SAS Institute Inc., Cary, NC, USA). Statistical support will be provided by [name].

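### The stated 12.5% improvement is 0.7625 s, but the sample size was computed for 0.8 s (13.1%); at 12.5% the power is about 76%, not 80%

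*Combined protocol and SAP*

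**What the plan says.** The sample size argument appears twice in the combined protocol and SAP, in section 1 (Sample size calculation) and in section 11.1, with nearly the same wording.

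- **Control mean.** The calculation is based on the proximal great saphenous vein (GSV): n = 174, median 6.1 s. No mean was found in the source, so the median is used instead. The reason given is that n is large, "according to the principle of the central limit theorem, so the gap between the median and mean is not large". Section 1 argues the same: "according to the principle of central limit theorem, such that the gap between the median and the mean is not large".
- **SD.** The table in section 11.1 gives SDs derived from ranges: 1.737 (proximal GSV), 1.921 (distal GSV) and 1.918 (small saphenous vein). The text concludes that "the standard deviation of the valve-carrying segments can be assumed to be approximately 1.8 overall".
- **Effect.** An improvement of roughly 10% to 15% is expected in the drug group, and "we decided to conservatively assume an improvement of 12.5% to calculate the number of participants". Section 1 says "we decided to conservatively assume an improvement of 12.5% to calculate the number of patients".
- **Calculation.** The PASS output, shown in section 1, has means 5.3 and 6.1, difference -0.8, SD 1.8, alpha 0.025 one-sided, 80 per group and actual power 0.80260. Section 11.1 reports that "the total number of participants was calculated as 160, with 80 participants in each group", raised to 200 for 20% dropout.
- **Analysis.** Section 11.2 states: "The primary outcome will be presented and compared between the two groups using an independent two-sample t-test".

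**The concern.** The text and the software output give two different design effects. The text says 12.5% of 6.1 s; the output uses 0.8 s, which is larger. The 80% power belongs only to the larger one. A reader who pairs the stated effect with the stated power will report 80% power for a 12.5% improvement, which the design does not have at the planned 80 evaluable patients per arm. That matters most if the result is null and the power statement is used to interpret it.

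Two supporting statements also mislead. Calling the effect conservative suggests a safety margin, yet 12.5% is the midpoint of the plan's own range and the value entered lies above that midpoint. The central limit theorem describes the sampling distribution of a mean. A large n does not bring the median and mean of a skewed distribution together, so 174 observations are no evidence that 6.1 s is close to the mean.

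**Working it through.** **Inputs.** Control mean 6.1 s, improvement 12.5% (expected range 10% to 15%), SD 1.8 s and tabled SDs 1.737, 1.918 and 1.921 (section 11.1). One-sided alpha 0.025, 80 evaluable and 100 recruited per arm (sections 1 and 11.1). PASS means 5.3 and 6.1 (section 1).

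**Formula.** z-test power = Φ(δ / (SD × √(2/n)) − 1.960). The t-test power uses the noncentral t distribution with 2n − 2 degrees of freedom and the same noncentrality.

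**1. The plan's own figure.** SD × √(2/n) = 1.8 × √(2/80) = 0.2846. With δ = 0.8, 0.8/0.2846 = 2.811, and Φ(2.811 − 1.960) = 0.8026. This reproduces the PASS value of 0.80260, so 0.8 s was the actual input and not a rounded display of 0.7625.

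**2. The effect stated in the text.** 6.1 × 0.875 = 5.3375 s, and 6.1 − 5.3375 = 0.7625 s. Rounding 5.3375 to 5.3 before subtracting gives 0.8 s, and 0.8/6.1 = 13.1%. The entered difference is 0.8/0.7625 = 1.049 times the stated one.

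**3. Power at the stated effect.** 0.7625/0.2846 = 2.679, and Φ(2.679 − 1.960) = 0.764.

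| n per arm | δ (s) | SD (s) | z-test | t-test |
|---|---|---|---|---|
| 80 | 0.80 (13.1%) | 1.8 | 80.3% | 79.8% |
| 80 | 0.7625 (12.5%) | 1.8 | 76.4% | 75.9% |
| 80 | 0.7625 (12.5%) | 1.737 | 79.3% | 78.8% |
| 80 | 0.7625 (12.5%) | 1.918 | 71.0% | – |
| 80 | 0.7625 (12.5%) | 1.921 | 70.9% | – |
| 100 | 0.7625 (12.5%) | 1.8 | 85.0% | 84.6% |

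**4. What 80% power requires.** The sum of the normal quantiles for alpha 0.025 and power 0.80 is 2.8016.

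- Smallest difference at n = 80, SD 1.8: 2.8016 × 1.8 × √(2/80) = 0.797 s, or 13.1% of 6.1 s.
- Largest SD at δ = 0.7625, n = 80: 0.7625 / (2.8016 × √(2/80)) = 1.721 s. Every SD in the plan's table is larger.
- Patients at δ = 0.7625, SD 1.8: 2 × (2.8016 × 1.8 / 0.7625)² = 87.5, so 88 per arm, or 88/0.8 = 110 recruited per arm at 20% dropout.

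**5. The expected range.** At 80 per arm and SD 1.8, z-test power is 57% for 10% (0.61 s) and 90% for 15% (0.915 s).

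**The case against.** The strongest reply is that this is a rounding difference of 0.0375 s in a study the plan calls exploratory. The value used, 13.1%, lies inside the expected 10% to 15%, and the PASS output shows its inputs openly. The other inputs are rougher than the gap. Across the tabled SDs, power at 12.5% runs from 79.3% to 70.9%, about twice the discrepancy. With the SD of the vein on which the calculation is based, the shortfall is only 0.7 points by the z-test. If 88 of 100 per arm are evaluable (12% dropout instead of 20%), power at 12.5% reaches 80%. The SDs also describe absolute reflux times, while the endpoint is a change, so no power figure here is firm.

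All of this bears on the size of the problem, and it is why the gap is called modest. It does not make the text and the output agree. None of the plan's SDs gives 80% at 12.5% with 80 per arm, and the plan itself assumes 20% dropout. Uncertain inputs are a reason to show power at both effects, not to attach one effect to the other's power. It is also fair to say that the word *conservatively* and the central limit theorem sentence are secondary: no power figure depends on them. Both are still incorrect as written.

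**Conclusion.** The concern holds. The plan states a 12.5% improvement but computed its power for 13.1%. At the stated effect, power is overstated by 3.9 points (80.3% against 76.4%, z-test) with the plan's SD of 1.8 s, and type II error is about 24% where the plan states 20%. These figures are conditional on the plan's own assumptions: control mean 6.1 s, equal SD of 1.8 s in both arms, one-sided alpha 0.025 and 80 evaluable patients per arm. The documents do not establish that this SD applies to the change in reflux time. This is an error of statement that should be corrected; it does not undermine the design or require a larger trial.

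**What to change.** Keep 200 patients. In sections 1 and 11.1, keep the sentence on the expected 10% to 15%, but replace the statement that 12.5% was used to calculate the number with wording such as:

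> Assuming an SD of 1.8 s and one-sided alpha 0.025, 80 evaluable patients per arm give 80% power for a difference of 0.80 s (13.1% of 6.1 s) and about 76% power for a 12.5% improvement (0.76 s).

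The old statement must be replaced, not left beside the new one, or the contradiction remains. The word *conservatively* goes with it. Delete the central limit theorem sentence in both places. The statements that the calculation uses the proximal GSV, and that a median stands in for a mean that was not found, can stay as a plain disclosure.

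The cost is one reworded sentence and two short deletions in each section, and a slightly less favourable power at 12.5%. No patients are added, and the endpoint, test and procedures do not change.
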